International Multicenter Double-blind Placebo-Controlled Parallel-Group Randomized Clinical Trial of Efficacy and Safety of Ergoferon in the Treatment of Viral Intestinal Infections in Children

Phase IV

Sponsor OOO «NPF «MATERIA MEDICA HOLDING»

Protocol number MMH-ER-008

Version date: November 02, 2015

ClinicalTrials.gov Id: NCT03039699

Protocol Summary

This document represents the protocol summary for the study on human subjects. The study will be carried out in accordance with ICH GCP, National Standard of the Russian Federation GOST 52379-2005 "Good Clinical Practice", Helsinki Declaration of World Medical Association, relevant requirements of the regulatory authorities as well as the study procedures.

Title of Study

International multicenter double-blind placebo-controlled parallel-group randomized clinical trial of efficacy and safety of Ergoferon in the treatment of viral intestinal infections in children.

Phase: IV

Sponsor: OOO "NPF "Materia Medica Holding", Moscow, Russia

Protocol No. MMH-ER-008

Objective of the study

• To obtain additional data on the efficacy and safety of Ergoferon in the treatment of viral intestinal infections in inpatient children.

Endpoints

Primary endpoint

1. Average diarrhea duration¹.

Secondary endpoints

- 1. Percentage of patients without diarrhea following 48, 72, and 96 hours of treatment.
- 2. Percentage of patients with recovery² following 48, 72, and 96 hours of treatment.
- 3. Average illness duration (from the enrollment to the recovery).
- 4. Total CDS score at 24, 48, and 72 hours after treatment initiation.
- 5. Average vomiting duration (if any).
- 6. Percentage of patients with negative PCR tests on Days 3, 4, 6, and 10 of observation versus baseline (no RNA detection of rotaviruses/ noroviruses/ astroviruses/ adenoviruses in patients who had positive tests at baseline).
- 7. Percentage of patients with worsening of illness³ and/or hospital-acquired infection⁴.

CONFIDENTIAL Page 2 of 14

¹ Diarrhea duration is considered as the time between receiving the first dose of investigational medicine /placebo and the normal consistency of stool pattern (to the previous stool consistency before diarrhea), i.e.

¹⁾ time to the first loose stool which is followed by two normal consistency stools over 24 h (infants may have three episodes of loose stool over a 24-hour period), or 2) time to ≤3 episodes of stool occurring over 24 h, at least 2 of which are normal consistency stools, or

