³⁾ time to the absence of stools for ≥ 12 h which is not followed by new episodes of diarrhea (total stool frequency over 24 h – less than 3 times).

² Recovery criteria: absence of diarrhea, vomiting, symptoms of dehydration, and increased body temperature (based on daily examinations by pediatrician).

³ Worsening of illness: an increase in dehydration scores and worsening of non-specific symptoms, as evidenced by a decline in general appearance, increasing fatigue and drowsiness, refusal to eat and drink, severe tachycardia/bradycardia, unstable hemodynamics, tachypnea, hypo- or hyperventilation, circulation disorders, peripheral cyanosis, sunken eyes, severe dryness of skin and mucous/tongue, poor tissue turgor, absent tears, persistent vomiting, anuria/acute kidney injury, seizure/convulsions, and meningismus.

⁴ Hospital-acquired infection: a viral or bacterial infection (intestinal, respiratory or urinary tract infection, etc.) occurring after at least 48 h of hospital stay and confirmed by laborator tests.

Safety assessment

- Adverse events (AE) during the treatment, AEs severity and relations to the study drug, and AEs outcomes.
- Changes in vital signs and laboratory parameters (complete blood count test, biochemistry blood test and urinalysis).
- Percentage of patients with abnormal biochemistry.

Study design

Study design: an international multicenter, double-blind, placebo-controlled, randomized clinical trial in parallel groups.

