⁶ The data of a patient whose PCR test indicates a bacterial etiology of acute intestinal infection will not be included in the analysis of treatment efficacy. For the sake of sufficiency of data for the efficacy analysis, it is statistically assumed that 50% of patients will test negative for viral etiology of acute intestinal infection.

pediatrician, and the examination results, including the CDS scores, will be recorded in source documents. The patient's parent/adopter will fill patient diary on a daily basis, recording the presence/absence of diarrhea signs, vomiting, and body temperature. The pediatrician will check correctness of diary filling. After discharge on day $10 \ (\pm 1)$ Visit 7 is scheduled (personal at the site/at home or distant/phone call) to interview the parents/adopters about the patient's health, presence of any complications, and use of medications (the investigator will fill out a questionnaire).

Collection of stool specimens and repeat PCR for Rotaviruses/Noroviruses/Astroviruses/Adenoviruses, Shigella spp., EIEC, Salmonella spp., and Campylobacter spp. will be performed on Days 3, 4, and 6 of inpatient observation and after discharge from the hospital (Day 10); collection of blood and urine specimens for safety tests will be carried out at baseline and before hospital discharge (day 6). The recording of the intake of study therapies and of concomitant medications as well as the assessment of compliance with and safety of the study therapies will be performed on Days 2-6 and 10.

Patients who recovered while in hospital and are discharged from the unit earlier than at 5 days will undergo the procedures of Visit 6, including the collection of biological specimens for PCR (efficacy evaluation) and biochemistry, blood test and urinalysis (safety assessment). The parents/adopters will be given the blister pack with the remaining study drug so that the patient can continue the treatment.

Inclusion and exclusion criteria

Inclusion criteria

- 1. Patients of either gender aged from 6 months to 6 years old hospitalized to infectious department.
- 2. Diarrhea (watery stool without visible abnormal foreign substances [transparent mucus is possible] ≥ 3 times a day).
- 3. Dehydration symptoms according to CDS scale ≥ 1 .
- 4. The first 48 hours from the onset of the first diarrhea episode.
- 5. Start of study treatment (Ergoferon/Placebo) within 12 hours after the start of the standard hospital therapy.

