Medical history	+						
Physical examination	+	+	+	+	+	+	
Body weight measurement	+					+	
Body length/height measurement	+						
Evaluation of dehydration symptoms using CDS	+	+	+	+	+	+	
Diary supply	+						
Checking the correctness of filling the diary		+	+	+	+	+	
Parent/adopter inquiry (personal/by phone) and filling questionnaire "Parent's/adopter's inquiry data"							+
Return of patient diary						+	
Concomitant therapy	+	+	+	+	+	+	+
Eligibility assessment	+						
Obtaining stool sample for PCR diagnosis	+		+	+		+	+*
Safety laboratory tests (hematology, serum chemistry,	+					+	

CONFIDENTIAL Page 9 of 14

urinalysis)							
Randomization and prescription of study drug	+						
Study drug supply							
, , , , , , , , , , , , , , , , , , ,	T .						
Basic medication supply	+	+	+	+	+		
Study drug accountability,						+ **	+ **
compliance assessment						Į.	!
Evaluation of treatment safety	+	+	+	+	+	+	+

^{*} All the subjects will receive sterile containers for stool storage and transportation on day 10. In case of a phone visit on day 10 stool samples will be delivered to the local laboratory by a courier.

Statistical Analyses.

Samples

Total set: all patients included in the study whose parents/adoptive parents signed the Informed Consent Form for the patient's participation in the study. All AEs including those occurred prior to the study therapy will be considered throughout the study for this sample.

Safety population: all patients who received at least one dose of the study drug. This sample will be used to *analyze the study treatment safety and tolerability*, since all the AEs identified after the study product administration will be recorded.

Full Analysis Set. This sample includes all enrolled and randomized patients, except for those who have experienced at least one of the following events:

- 1) non-compliance with inclusion / exclusion criteria;
- 2) the patient has not taken a single dose of the study drug;
- 3) lack of any data of the patient following randomization;
- 4) withdrawal of a patient due to early discharge (discharge of patient with persistent symptoms of acute intestinal infections on days 2-5 of hospitalization before the study treatment is completed at the parent's/adopter's request).

This sample is the most consistent with the "Intention-to-treat" principle, will be used for the *Intention-to-treat analysis (ITT analysis) of the the study therapy efficacy*.

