Per protocol set. This sample includes all patients who completed the therapy as per the study protocol without any missing visits or significant protocol deviations. This sample will be used for the *Per Protocol analysis (PP- analysis) of the the study therapy efficacy*.

Mean value in Placebo group for the relevant day will be used to fill lacking/missing data.

Data treatment and all statistical calculations under the protocol will be made using SAS-9.4 statistical software¹⁰.

CONFIDENTIAL Page 10 of 14

^{**} Return of the study product is made after 5-day treatment course (on Day 6). If the subject is discharged sooner than on day 6, the parent/adopter will be given a blister with the remaining product to complete outpatient therapy; in this case the product return and determination of compliance will be made on Day 10 ± 1 .

¹⁰ Holder of license: OOO "NPF "Materia Medica Holding", No. 70100045.

Evaluation of sample size

The sample size has been assessed on the basis of the following rules and assumptions:

- 1. Statistical provisions.
 - 1.1 the power of the statistical tests " $P = (1 \beta)$ " is assumed to be 80% (the probability of correct rejection of the null hypothesis is 0.8);
 - 1.2 the probability of a type I error " α " is allowed to be less than 5% (the probability of the erroneous acceptance of an alternative hypothesis is less than 0.05);
 - 1.3 the statistical criteria are 2-sided;
 - 1.4 the calculation of the sample size is based on the assumptions about the expected effects, mainly declared in the primary efficacy criterion of the Protocol;
 - 1.5 statistical null and alternative hypotheses are formulated as follows:

$$H_0: m_2-m_1 \le 0$$

$$H_1: m_2-m_1>0,$$

where $\mathbf{m_1}$ – mean disease duration in Ergoferon group,

m₂ – mean disease duration in Placebo group;

- 1.6 to assure potential adjustment of sample size or terminate the study due to inadequate efficacy/high efficacy, interim analysis will be carried out in which:
 - a. calculations will be made using O'Brien-Fleming boundary;
 - b. proportions of the subjects completing the study and yielding the results for interim and final analyses, will be taken as 0.5 and 1.0 (i.e. interim analysis will be made after recruitment of half of the planned number of the clinical study subjects.
- 1.7 therefore, sample size will be calculated taking into account
 - a. interim analysis;

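### No timed stool record is planned after Visit 6, so the end or return of diarrhea after that point cannot be dated, although follow-up runs to Day 10

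*Combined protocol and SAP*

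**What the plan says.** The primary endpoint is "Average diarrhea duration", counted from the first dose (Endpoints, footnote 1). Criteria 1 and 2 for its end each use a 24-hour window. Criterion 3 is "time to the absence of stools for ≥ 12 h which is not followed by new episodes of diarrhea". Secondary endpoints include freedom from diarrhea and recovery after 48, 72 and 96 hours. Footnote 2 bases recovery on daily examinations by the pediatrician.

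Under Study design, parents fill in the diary every day, "recording the presence/absence of diarrhea signs, vomiting, and body temperature". The Schedule of study procedures marks "Return of patient diary" under Day 6 only. Collection of complaints, physical examination and dehydration scoring are marked for Days 1 to 6.

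For early discharge, Study design states: "Patients who recovered while in hospital and are discharged from the unit earlier than at 5 days will undergo the procedures of Visit 6". The double-asterisk note to the schedule makes one exception for these children: "the product return and determination of compliance will be made on Day 10" (±1). It does not mention the diary.

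Follow-up lasts 10 days. On Day 10±1 the investigator is "to interview the parents/adopters about the patient's health, presence of any complications, and use of medications" and fills in a questionnaire. That visit also has a stool PCR sample, concomitant therapy and a safety evaluation. There is no rule for diarrhea still present when Visit 6 takes place. The Samples section has only a general rule that missing data are filled with the placebo mean for the day.

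**The concern.** The primary endpoint is a time, so it needs dated stool observations until the episode is over and, under criterion 3, some observation afterwards. The plan keeps contact with every child to Day 10 but schedules nothing after Visit 6 that is shown to date a loose stool.

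Two groups are affected.

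- **Recovered children discharged early.** Their diary cover ends soonest. The no-new-episodes condition of criterion 3 cannot be checked against a timed record, and any of the 48, 72 or 96 h assessments that fall after discharge have no planned timed source.
- **Children still ill near Day 6.** Their diarrhea ends outside the recorded window, so the duration is known only to exceed some value.

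A scoring or censoring rule can say how to treat such children, but it cannot supply an end time or a recurrence time that was never collected.

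**Working it through.** **Planned inputs.** Evaluation of sample size gives a 12 h difference, SD 36 h (1.5 d), two-sided 5% and 80% power. These reproduce the plan's group size: 2 × 36² × (1.960 + 0.842)² / 12² = 141.3. Multiplying by the two-look O'Brien-Fleming factor of 1.0078 gives 142.4, hence 143 per group; half is 71.5, hence 72 at the interim. The point below does not alter these figures.

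**Length of cover (assumption).** From Day 1 to the same clock time on Day 6 is 5 × 24 = 120 h.

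- Latest end that can be confirmed under criteria 1–2: 120 − 24 = 96 h.
- Latest end under criterion 3, counting only its 12 h stool-free period: 120 − 12 = 108 h.

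**Duration model (assumption).** Lognormal or gamma, matched to mean m and SD s. For the lognormal, σ² = ln(1 + s²/m²) and μ = ln m − σ²/2. The plan gives no arm means with its 12 h difference, so I used two pairs with SD 1.5 d: 2.4 v 2.9 d (footnote 11's placebo mean less 0.5 d) and 1.9 v 2.4 d (footnote 11's active mean plus 0.5 d). Footnote 11 itself reports 1.9±1.2 v 2.9±1.8 d, for a different product, in rotavirus infection.

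**Formulas.** S(T) is the share still with diarrhea at T.

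- Late children counted at the limit: mean = ∫₀ᵀ S(t) dt.
- Late children dropped: mean = [∫₀ᵀ S(t) dt − T·S(T)] / [1 − S(T)].

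**Worked case** (2.4 v 2.9 d, lognormal, T = 5 d):

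- Ergoferon: σ = 0.574, μ = 0.711, so S(5) = 1 − Φ((1.609 − 0.711)/0.574) = 0.059.
- Placebo: σ = 0.487, μ = 0.946, so S(5) = 0.087.
- Counted at the limit: means 2.308 and 2.780 d; difference 0.472 × 24 = 11.3 h.
- Dropped: means 2.140 and 2.569 d; difference 0.429 × 24 = 10.3 h.

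**All cases at T = 5 d** (ranges span the two shapes):

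| Scenario | Still ill, Ergoferon/active | Still ill, placebo | True difference | Counted at limit | Dropped |
|---|---|---|---|---|---|
| Plan, 2.4 v 2.9 d | 5.9–6.3% | 8.7–9.3% | 12 h | 11.3 h | 10.1–10.3 h |
| Plan, 1.9 v 2.4 d | 4.1–4.4% | 5.9–6.3% | 12 h | 11.6 h | 10.9 h |
| Footnote 11 | 2.2–2.5% | 10.8–12.2% | 24 h | 20.2 h | 14.2–15.5 h |

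On the plan's figures this is about 6–9 of 143 Ergoferon children and 8–13 of 143 placebo children.

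**Relapse after early discharge.** No calculation is possible, because the documents give neither a relapse rate nor the distribution of discharge days.

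**The case against.** The strongest reply is that nothing shows the information is lost. The document is a protocol summary and does not list the items on the Day 10 questionnaire. Persisting or returning diarrhea fits naturally under the child's health, and the safety evaluation could also catch it. This stands in part: a reader might infer that late or relapsing diarrhea goes wholly unrecorded, and the documents do not support that. What remains is that recall at Day 10 is not shown to yield a time.

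Two links are inferences. No passage names the diary as the source of the primary endpoint; however, the daily examinations end at the same visit, so they do not close the gap. Nor does the plan say outright that the diary is returned at early discharge. It follows from "discharged from the unit earlier than at 5 days will undergo the procedures of Visit 6" together with a note that exempts only the study product and compliance.

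The early-discharge gap is also limited. It concerns children judged recovered, because those taken home with symptoms at the parent's request are withdrawn and left out of the Full Analysis Set. A relapse alters the primary endpoint mainly through criterion 3.

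A reader might take 96 h as a hard ceiling. It is not, since criterion 3 reaches about 108 h. A child first dosed at 20:00 on Day 1 reaches 96 h at 20:00 on Day 5, and a Visit 6 at 08:00 still allows 12 h.

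Finally, the larger losses on footnote 11's figures arise from dropping late children, which the plan does not prescribe. Counting them at the limit retains 20.2 of 24 h.

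**Conclusion.** The gap is real but modest. After Visit 6 no stool-level record is planned, and the Day 10 interview is not shown to capture when diarrhea ended or recurred. With about 120 h of cover and lognormal or gamma durations, about 4–6% of Ergoferon and 6–9% of placebo children would still have diarrhea on the planned assumptions (2–3% and 11–12% on footnote 11's figures). The planned 12 h difference would appear as 11.3–11.6 h if these children are counted at the limit, or about 10–11 h if they are dropped.

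A reader might go on to infer lost power, a bias that favours Ergoferon, or a false-positive risk. None of these is shown. Capping long durations also reduces the SD, and the same observation schedule applies to both blinded arms. The effect of missed relapse has no size or direction that the documents can support. Nor do the children beyond Day 5 carry most of the treatment difference: when late children are counted at the limit, time past 5 days holds (12 − 11.3)/12, about 6%, of the planned difference at most, and (24 − 20.2)/24, about 16%, of footnote 11's. This is therefore a cheap improvement to collection of the primary endpoint, not an error that invalidates the design.

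**What to change.** 1. In the Schedule of study procedures, move the diary-return mark from Day 6 to the Day 10±1 column, and say in the double-asterisk note that early-discharged children keep the diary.
2. Have parents continue the stool, vomiting and temperature entries at home until Visit 7.
3. Add to the existing Day 10 parent questionnaire the date and time of the last loose stool and of any recurrence.
4. State that diarrhea duration and the 48, 72 and 96 h status are derived from the whole Day 1–10 record.

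The cost is an amendment to the schedule table, diary instructions and questionnaire. No visit is added, because Visit 7, the questionnaire, the Day 10 product return for early-discharged children and the Day 10 stool collection already exist. The downside is about four more days of parent entries (more after early discharge), unsupervised and in part of lower quality.

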- 4. The patient's or his/her parent/adopter wish to complete the study ahead of schedule for any reason.

CONFIDENTIAL Page 5 of 14

_

⁷ Criteria for a severe intestinal infection: sudden patient deterioration, sudden fatigue or even adynamia, marked apathy and drowsiness/excessive sleepiness and lethargy, dry mucous membranes, sunken eyes, loss of tearing, pool tissue turgor, lack of eye contact in the child on examination, aversion to food and drink, severe tachycardia/bradycardia, unstable hemodynamics, tachypnea, hypo- or hyperventilation, impaired microcirculation, peripheral cyanosis, slow capillary nail refill, persistent vomiting, anuria/acute renal disease, convulsions, and meningism.

- 5. Cases not specified by the protocol when, according to the investigator's opinion, further participation in the study harms the patient.
- 6. Incorrect inclusion of ineligible patient.
- 7. Early discharge of patient from hospital with persisting acute intestinal infection symptoms on days 2-5 of hospitalization, before the end of taking the study therapy at the parent's/adopter's request.

Number of subjects

It is planned to enroll 572 patients, which is expected to allow completion of all protocol procedures by at least 286 PCR-positive (for viral acute intestinal infection) patients (143 patients in the Ergoferon and Placebo groups).

Interim analysis

An interim statistical analysis will be performed as part of this study.

The interim analysis will be based on the patient assessment data and treatment outcomes recorded for the protocol-defined number of patients who have completed participation in the study.

Number of patients to be evaluated in the interim analysis:

144 patients (72 in the Ergoferon group and 72 in the Placebo group).

Number of patients to be evaluated in the final analysis:

286 patients (143 in the Ergoferon group and 143 in the Placebo group).

Treatment

Group 1

Name of the medicinal product: Ergoferon

Active ingredient: affinity purified antibodies to human gamma interferon -0.006 g*, affinity purified antibodies to histamine -0.006 g*, affinity purified antibodies to CD4 -0.006 g*

* Mixture of water-ethanol dilutions 100^{12} , 100^{30} , 100^{50} of active substance used for saturation of lactose monohydrate.

Excipients: Lactose monohydrate -0.267 g, microcrystalline cellulose -0.03 g, magnesium stearate -0.003 g.

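### The Full Analysis Set used for the ITT efficacy analysis drops dosed children taken home on Days 2-5 with symptoms persisting but keeps those discharged because they recovered

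*Combined protocol and SAP*

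**What the plan says.** Statistical Analyses, Full Analysis Set, starts from all randomized patients and removes four groups: ineligible, never dosed, no data after randomization, and (item 4) "withdrawal of a patient due to early discharge (discharge of patient with persistent symptoms of acute intestinal infections on days 2-5" of hospitalization, at the parent's request and before treatment is complete. The section then states: "This sample is the most consistent with the 'Intention-to-treat' principle", and assigns the set to the ITT efficacy analysis.

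Criteria for Withdrawal or Termination, item 7, makes the same event a reason for withdrawal: "Early discharge of patient from hospital with persisting acute intestinal infection symptoms on days 2-5 of hospitalization".

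Recovered children who go home early are handled differently. Study design says: "Patients who recovered while in hospital and are discharged from the unit earlier than at 5 days will undergo the procedures of Visit 6". They take the remaining drug home and meet none of the four exclusions.

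The only other efficacy set, the per-protocol set, takes children who completed therapy with no missing visits or significant deviations. The Total set and the Safety population contain the removed children, but their stated uses are adverse events and safety.

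On available data, the parent "will fill patient diary on a daily basis, recording the presence/absence of diarrhea signs, vomiting, and body temperature", and a pediatrician examines the child daily in hospital. The Day 10 interview covers the child's health, "presence of any complications, and use of medications (the investigator will fill out a questionnaire"; no date for the end of diarrhea is listed.

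**The concern.** Never-dosed children and children without data are already covered by items 2 and 3. What item 4 adds is the removal of dosed children who do have data, because they were still unwell when they left. Two children leaving on the same day are kept or deleted according to clinical status, and clinical status is closely tied to the primary endpoint (diarrhea duration) and to the recovery endpoints. Withdrawals for an adverse event, for prohibited medication or at the parent's wish are not FAS exclusions in themselves, so the outcome-linked reason is the one singled out.

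Two things are at stake. Within each arm, deleting children who are still ill shortens mean duration and raises the 48, 72 and 96 h rates. Between arms, the comparison loses the protection of randomization if take-home rates differ. The report would also describe as ITT an analysis that omits randomized, treated children, with no other efficacy analysis to show whether they matter.

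**Working it through.** **1. The plan's own sample size.** Inputs from Evaluation of sample size: difference 12 h, SD 36 h, two-sided 5%, power 80%, O'Brien-Fleming looks at 0.5 and 1.0.

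- Fixed design: n = 2 × 36² × (1.960 + 0.842)² / 12² = 141.28 per group.
- Two-look inflation factor 1.0078: 142.38, rounded up to 143. Half is 71.19, rounded up to 72.
- Enrolled: 286 / (1 − 0.5) = 572.

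All the stated figures reproduce. The target counts per-protocol completers, so item 4 does not affect it.

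**2. Is there an early-discharge rate?** No. The 50% coefficient combines negative PCR results, screening failures and withdrawals. Everything below is therefore an assumed range.

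**3. Model.** Duration is taken as lognormal with the placebo figures of footnote 11: 2.9 × 24 = 69.6 h and 1.8 × 24 = 43.2 h. Then σ² = ln(1 + (43.2/69.6)²) = 0.3259, σ = 0.5709 and μ = ln 69.6 − 0.3259/2 = 4.0798. A still-ill child is taken home with probability h at each of 24, 48, 72 and 96 h, so a child ill at k of these checks is kept with probability (1 − h)^k. Both arms have the same durations (the null), and the persisting symptom is taken to be diarrhea.

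| Duration band | k | Share | Mean in band |
|---|---|---|---|
| up to 24 h | 0 | 5.71% | 19.2 h |
| 24-48 h | 1 | 30.03% | 36.8 h |
| 48-72 h | 2 | 27.75% | 59.2 h |
| 72-96 h | 3 | 16.71% | 82.8 h |
| over 96 h | 4 | 19.80% | 137.3 h |

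**4. Equal rates, h = 5%.**

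- Kept: 0.0571 + 0.2853 + 0.2504 + 0.1433 + 0.1613 = 0.8974, so 10.3% are deleted.
- Kept mean: (1.10 + 10.50 + 14.83 + 11.87 + 22.14) / 0.8974 = 67.3 h, against 69.6 h.
- Diarrhea-free at 72 h: (0.0571 + 0.2853 + 0.2504) / 0.8974 = 66.1%, against 63.5%.
- Both arms shift alike, so the between-arm difference is zero.

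**5. Unequal rates.** The same sums give the table below. Type I error was simulated with 143 randomized per arm, using the t-test and Mann-Whitney test at a single nominal two-sided 5% level.

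| Rate per day | Deleted | Kept means | Spurious difference | Type I error |
|---|---|---|---|---|
| 2% vs 1% | 4.2% vs 2.1% | 68.7 vs 69.2 h | 0.5 h | about 5% |
| 6% vs 3% | 12.2% vs 6.3% | 66.9 vs 68.3 h | 1.4 h | about 6% |
| 10% vs 5% | 19.6% vs 10.3% | 65.0 vs 67.3 h | 2.3 h | 7-8% |

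The arm losing more children looks better. Swapping the rates reverses the sign.

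**6. Sensitivity of these figures.**

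- Gamma durations with SD 36 h and a constant leaving rate between 24 and 120 h give 2.0 h and 7.8% at 10% vs 5%.
- Recovery also requires no vomiting, dehydration or fever (Endpoints, footnote 2), so a removed child may already be free of diarrhea. If 13% or 22% are, the 2.3 h becomes 1.8 or 1.4 h.
- With a true 12 h benefit and equal rates of 5% or 10%, the observed lognormal difference is 11.6 or 11.2 h (SD 36 active, 43.2 placebo), 12.1 or 12.2 h (SD 36 in both) and 11.1 or 10.2 h (SD 28.8 and 43.2). The change is modest and its direction depends on the SDs.

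**The case against.** The strongest reply is that all the between-arm bias comes from an assumed 2:1 ratio of take-home rates in a trial with no effect on duration. The trial is double-blind, and the placebo has the same description and excipients. The documents point to no reason why parents in one arm should leave more often. A difference in tolerability, or an effect on symptoms other than diarrhea, could produce one, but that is only a possibility. This stands: existence and size of bias are unproven, and even at 6% vs 3% the inflation is small.

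A second reply is that the sample size is built on the per-protocol set, which omits these children anyway, and that the documents do not say which efficacy set is primary. That also stands, so an effect on the trial's main conclusion is not established. It does not rescue the FAS, whose purpose is to show what happens when such children are kept.

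A third reply is that the remedy can be worse than the rule. Suppose leaving is four times as likely within 24 h of resolution, under the null with base rates of 10% vs 5%. Kaplan-Meier then gives differences of −1.8, −2.5 and −2.3 points at 48, 72 and 96 h, against +1.3, +0.9 and +0.3 under the current rule. This is a fair warning. It argues for confining the censored analysis to FAS duration and recovery time and pairing it with a sensitivity analysis, not for deleting the children.

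A reader might infer that item 4 tilts the trial toward Ergoferon. The documents do not support that: the bias can go either way and is nil under the null at equal rates. Nor should 286 per arm be used to claim larger inflation. That is the number enrolled, before bacterial cases, negative PCR results and screening failures are taken out, whereas the final analysis is planned on 143 per group.

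**Conclusion.** The point holds as one of definition. The set used for the ITT efficacy analysis is selected on a post-randomization, outcome-related event, and no other efficacy set or imputation rule restores the removed children: the per-protocol set leaves them out, and the placebo-mean fill cannot reach children outside the set. This rests on the text and is firm.

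The size is conditional. Within-arm results look somewhat better than they should whenever the persisting symptom is diarrhea. Between-arm bias under the null arises only if take-home rates differ, and over the range examined it runs from about 0.5 to 2.3 h against a planned effect of 12 h. These figures rest on assumed discharge rates, a lognormal shape and leaving that depends only on being still ill. The 143 per group and 572 enrolled stand. It should be fixed, but it does not by itself invalidate the trial.

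**What to change.** - Delete item 4 from the FAS exclusions. It may stay as a per-protocol exclusion.
- Report the number of such discharges by arm and day.
- In the FAS, where the end of diarrhea or recovery was met before discharge, use it as observed. Otherwise right-censor duration at the last recorded status, using the survival methods already listed under Non-parametric criteria (LIFETEST).
- State in advance how a discharge inside a confirmation window of Endpoints, footnote 1, is treated. One criterion needs "episodes of stool occurring over 24 h, at least 2 of which are normal consistency stools"; another needs a 12 h absence of stools "which is not followed by new episodes of diarrhea".
- State that the placebo-mean fill does not apply to these children.
- Keep the planned comparison of means in the per-protocol set.
- Because discharge may be related to later course, prespecify one sensitivity analysis that counts unresolved discharges as not resolved, or not recovered, at later time points.

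The cost is mainly SAP wording. No new measurement is needed, but the diary must be collected at discharge, since the schedule lists its return on Day 6. The FAS analysis of duration would no longer test the difference in means directly (Evaluation of sample size, 1.5), and it assumes that discharge is non-informative among children still ill. Reported rates would be slightly less favourable.
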